11.1.8 Neurological Examination

A Neurologic Examination including light touch and pinprick sensation, vibratory sensation, deep tendon reflexes, and strength assessments will be performed at the times indicated in [Table 2](#). The Neurologic Examination will be done during "On" time.

Any abnormalities or symptoms identified during treatment will be recorded as adverse events.

The neurological examination will assess:

- Cranial nerves – assessment of cranial nerves II–XII, excluding fundoscopic examination
- Motor system – assessment of tone, strength and abnormal movements
- Sensory system – including light touch, pinprick, joint position and vibratory sense
- Reflexes – assessment of deep tendon reflexes and plantar responses (Babinski sign)
- Coordination – assessment of upper and lower extremities
- Gait – assessment of base and tandem gait
- Station – assessment of posture and stability

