12.1.1 Recording of Adverse Events

All AEs should be recorded on the Adverse Events eCRF and source documents.

In addition Product Quality Complaints concerning devices, cassettes, and/or LCIG should be recorded on the Product Quality Complaint and Incident form, and the source documents. Product Quality Complaints must be reported immediately (within 24 hours of the study site's knowledge of the event) by fax to Quintiles Pharmacovigilance (Pharmacovigilance fax numbers are found in Section [12.2.1](#)). Product Quality Complaints concerning devices should also be recorded on the eCRF. Product Quality Complaints leading to a subject's health impairment should be recorded in the eCRF as an AE.

In order to avoid vague, ambiguous or colloquial expressions, the AE should be recorded in standard medical terminology rather than the subject's own words. Whenever possible, the Investigator should group together the signs and symptoms which constitute a single diagnosis into a single term which reflects the actual diagnosis.

The existence of or change in an AE may be concluded due to the necessity to administer a concomitant medication, from a spontaneous report of an event from the subject, from the physical examination or from the results of special tests such as ECG, electroencephalograms, laboratory assessments or other study- specified tests (source of AE).

AEs which occur in the specified pre-treatment through the follow-up period, regardless of the interval prior to the first administration of the study drug or the interval since the last administration of the study drug, will be handled as any other AE occurring during the treatment with study drug. Following termination of LCIG treatment, including the removal of PEG-J, AEs should continue to be reported for 30 days, irrespective of the reason for termination (Early Termination or the end of the study).

Each AE is to be evaluated for duration, severity, seriousness and causal relationship to the therapeutic system. The action taken with the therapeutic system, the concomitant treatment/therapy introduced and the outcome, as well as whether the event led to study termination, will also be recorded.

Severity

The severity of the AE should be characterized as "mild, moderate or severe" according to the following definitions:

- Mild events are usually transient and do not interfere with the subject's daily activities.

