13.3 Statistical Methods

Safety Analysis

The Safety Population will be used for the analysis of the safety and tolerability data.

Adverse events will be coded using the Medical Dictionary for Regulatory Activities (MedDRA). A treatment-emergent adverse event (TEAE) is defined as any adverse event that begins or worsens in severity on or after the first dose of study drug in the current study and within 30 days of the end of LCIG treatment in the current study. For subjects transferring to commercial product, the end of treatment in the current study will be the last dose of study drug. For subjects who are discontinuing LCIG treatment, the end of treatment in the current study will be the removal of the PEG-J tube. The following summaries of TEAE's will be prepared:

- Incidence of treatment-emergent adverse events
- Incidence of treatment-emergent serious adverse events

- Incidence of treatment-emergent adverse events resulting in study termination
- Incidence of treatment-emergent adverse events of special interest

The following additional analyses of safety will also be prepared:

- Summary of vital sign and weight values and mean change from Baseline over time
- Incidence of potentially clinically significant vital sign and weight values
- Summary of clinical lab values and mean change from Baseline to Endpoint
- Summary of special lab values and mean change from Baseline over time
- Incidence of potentially clinically significant clinical lab values
- Summary of MIDI at Baseline and during treatment
- Summary of C-SSRS
- Incidence of device complications

Efficacy Analysis

The Efficacy Population will be used for analyses of efficacy. The mean change from baseline to endpoint will be summarized for the following efficacy endpoints.

- "Off" time as measured by the Parkinson's Disease Diary
- "On" time without troublesome dyskinesia (sum of "On" time without dyskinesia and "On" time with non-troublesome dyskinesia) as measured by the Parkinson's Disease Diary
- UPDRS total score, Parts I, II, III and IV scores, and dyskinesia item score
- PDQ-39 summary index and domain scores

For the analysis of change from baseline in efficacy measures, each subject's baseline will be their baseline measure in the first LCIG study in which they participated (e.g., Study S187.3.001, S187.3.002 or S187.3.004).

Additional Analysis

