8.5 Safety Analysis Variables

8.5.1 Adverse Events

Adverse event (AE) Investigator terms are assigned to a Lowest Level Term (LLT) and a Preferred Term (PT) and will be classified by High Level Term (HLT), High Level Group

Term (HLGT) to one System Organ Class (SOC), namely the primary SOC, according to the MedDRA thesaurus, Version 14.0.

AE Investigator terms that are related to procedural or device complications may also have a secondary coding. For example, consider the verbatim term "Worsening of Parkinson's disease due to PEG-J dislocation." This AE can be coded as follows:

Primary Coding –

- Lower Level Term: 'PARKINSONISM AGGRAVATED'
- Preferred Term: 'PARKINSONISM'
- System Organ Class: 'NERVOUS SYSTEM DISORDERS'

Secondary Coding –

- Lower Level Term: 'DEVICE DISLOCATION'
- Preferred Term: 'DEVICE DISLOCATION'
- System Organ Class: 'INJURY, POISONING AND PROCEDURAL COMPLICATIONS'

AE summaries will include the primary as well as the secondary coding.

A detailed description of each AE includes:

- The start and stop date of the event or "Ongoing" at the end of the study.
- Severity (categorized as "Mild," "Moderate" or "Severe"). If severity is missing it will be regarded as "Severe."
- Relationship to the investigational therapeutic system (categorized as "Unrelated," "Unlikely," "Possible" or "Probable").
- Action taken with investigational study medication:
 - Drug discontinued.
 - Drug interrupted.
 - Dosage reduced.

- Dosage increased.
- None/not applicable.
- Outcome of event, which is defined as any one of the following:
 - Recovered/Resolved.
 - Recovered/Resolved with Sequelae.
 - Fatal.
 - Unknown.

If an adverse event is "Ongoing," the Outcome will be blank.

- Serious, categorized as "Yes" or "No."
- Concomitant treatment/therapy introduced, categorized as "Yes" or "No."
- Led to study termination, categorized as "Yes" or "No."

Missing and/or incomplete dates for AEs are imputed in a manner resulting in the earliest onset within the Treatment Period and the longest duration. However, the Stop Date will not be imputed if the event is reported as "Ongoing."

Technically, this will be done as follows:

For a missing/incomplete start date the minimum of the following will be imputed:

- The maximum of the earliest possible start date and the date of first administration of investigational study drug
- The latest possible start date
- The latest possible stop date

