For a missing/incomplete stop date the maximum of the following will be imputed:

- The minimum of the latest possible stop date and the date of last administration of investigational study drug
- The earliest possible stop date
- The earliest possible start date

Here, the earliest (latest) possible date is defined as:

- The date itself if it is possible
- The date of the first (last) day of the month, if month and year are available but the day is missing
- The date of the first (last) day of the year, if year is available but day and month are missing
- A very early (late) date, for example, 01JAN1000 (01JAN3000), if the date is completely missing

From this data the following will be determined and used for presentation in the applicable tables and listings:

- Treatment-Emergent Adverse Events (TEAEs): Defined as AEs which started on or after the Date of the First 3005 LCIG Infusion and within 30 days of the Date of the Last 3005 PEG-J Exposure.
- Treatment-Emergent Serious Adverse Events (TESAEs): Defined as TEAEs regarded by the Investigator as Serious.
- TEAEs that are at least possibly related to the therapeutic system: Defined as TEAEs assessed as having a "Possible" or "Probable" relationship to the investigational therapeutic system and includes those events where the relationship is missing.
- Severe TEAEs: Defined as TEAEs assessed as being "Severe" in intensity and includes those events where the severity is missing.
- TEAEs that led to premature discontinuation: Selected as those events where: "Led to Study Termination" is indicated as "Yes."
- TEAEs with fatal outcome as reported on the "Adverse events" CRF.
- TEAEs in the following categories have been defined as TEAEs of special interest:
 - Procedure and device associated events
 - Polyneuropathy (broad search as well as narrow search)
 - Weight loss

- Cardiovascular fatalities
- Respiratory tract aspiration including aspiration pneumonia/pneumonitis

TEAEs are included in a category of special interest based on their PT and, in the case of cardiovascular fatalities, their outcome. The list of PT's assigned to each category is included as Appendix 12.4. Only TEAEs where an outcome of "Fatal" has been reported on the "Adverse Event" CRF are to be included in the category of cardiovascular fatalities. All events with PT's other than those assigned to the procedure and device associated AESI category will be included in summaries of events that are not procedure and device related.

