The percentage of each of the aforementioned AE types will be determined as the number of subjects with at least one mention of the AE type relative to the number of subjects at risk. A subject will be considered at risk if the subject is in the Safety subject sample.

In addition to the aforementioned AE types, AEs reported by the Investigator as related to device complications will also be summarized. Device complications are captured in the DE raw data panel and associated AEs are captured in the AE raw data panel.

Investigators link the AEs that are related to device complications by entering an AE number in the DE raw data panel.

The incidence and prevalence of TEAEs during each 3005 Treatment Year will be summarized using the study day intervals described in Section 6.4.9. AE start days and Treatment Period end days will be calculated relative to the start of 3005 LCIG infusion (RFSTDTN) as follows:

$$\text{AE Start Day} = (\text{AE Start Date} - \text{Date of First 3005 LCIG Infusion}) + 1$$

$$\text{Treatment Period End Day} = ([\text{Date of Last 3005 PEG-J Exposure} + 30 \text{ Days}] - \text{First Date of 3005 LCIG Infusion}) + 1$$

For summaries of incidence, the count (and numerator for percentage calculations) will be the number of subjects who had their first treatment-emergent occurrence of the PT start

within the study day range for the 3005 Treatment Year. Each subject will be counted at most once within each SOC and PT.

For summaries of prevalence, the count (and numerator for percentage calculations) will be the number of subjects who had a treatment-emergent occurrence of the PT start within the study day range for the 3005 Treatment Year or who had an earlier treatment-emergent occurrence of the PT that had not ended prior to the start of the study day range for the 3005 Treatment Year.

The denominator for both incidence and prevalence percentage calculations will include all subjects whose Treatment Period End Day is within or greater than the study day range for the 3005 Treatment Year.

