8.5.5.7 Neurological Examination

At each of the scheduled visits indicated in the flowchart of study assessments a neurological examination will be performed including light touch and pinprick sensation, vibratory sensation, deep tendon reflexes, and strength assessments. Any abnormalities or symptoms identified will be reported as adverse events.

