10.0 Changes to Planned Analyses

10.1 Changes to the Analysis as Laid Down in the Protocol and Amendments

The protocol statistical methods (Section 6.2 and Section 13.3) stated that for the analysis of change from baseline in efficacy measures, each subject's baseline will be their baseline measure in the first LCIG study in which they participated (e.g., Studies S187.3.001, S187.3.002 or S187.3.004). To focus the analysis on the maintenance of efficacy during participation in Study 3005, each subject's baseline value for the analysis of change from

baseline in efficacy measures will be the final value in the preceding open-label study. To provide context, the change in each efficacy measure from initial LCIG infusion to 3005 endpoint will also be determined and summarized.

Protocol Section 12.1.4 identifies the following as adverse events of special interest:

- Risks of PEG-J insertion
- Long-term complications of PEG-J
- Device-associated gastrointestinal disorders during long-term therapy

For consistency with current practice throughout the LCIG development program, these 3 categories have been combined into a single category of procedure and device associated events (Duodopa product specific CMQ).

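### SAP 8.5.1 defines treatment-emergent AEs by start date only and drops the protocol's worsening-in-severity limb without declaring it; the number of events lost is unknown and may be zero

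*SAP*

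**What the plan says.** Protocol 13.3 defines a TEAE as "any adverse event that begins or worsens in severity on or after the first dose of study drug in the current study", up to 30 days after the end of LCIG treatment. Appendix B shows the worsening wording both before and after the last amendment, so it is neither superseded nor newly inserted text. The SAP introduction says that the SAP incorporates Global Amendments 1 to 4.

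SAP 8.5.1 says TEAEs are "Defined as AEs which started on or after the Date of the First 3005 LCIG Infusion and within 30 days of the Date" of last PEG-J exposure. Serious, severe, related, fatal and special-interest TEAEs are then defined as subsets of that group.

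SAP 10.1 declares two departures from the protocol. One is the efficacy baseline. The other is the grouping of three special-interest categories: "For consistency with current practice throughout the LCIG development program, these 3 categories have been combined into a single category". The TEAE definition is not among them.

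**The concern.** Protocol 13.1 makes long-term safety the primary statistical objective, and the TEAE flag decides what enters almost every adverse event table. Subjects come from earlier studies with LCIG and a PEG-J already in place, so a condition present at entry that becomes more severe is a plausible kind of event. The categories of special interest in protocol 12.1.4 include long-term PEG-J complications and possible precursors of polyneuropathy, where worsening matters.

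The start-only rule can only lower counts. Elsewhere the SAP leans the other way: missing severity is taken as severe, missing relationship as related, and AEs starting on Day 1 are assigned to treatment. A reader cannot tell whether the worsening limb was dropped by choice or by oversight.

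**Working it through.** There is no figure in the plan to reproduce. The check sets the two rules side by side and then asks how far the difference reaches.

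**1. Does anything else in the SAP restore worsening?** No. Section 6.4.6 assigns AEs to the Treatment Period by start. The by-year incidence rule in 8.5.1 uses the AE start day. The prevalence rule reaches back only to subjects "who had an earlier treatment-emergent occurrence of the PT that had not ended prior to the start of the study day range", so TEAE status is needed first. Section 9.11.1 inherits the label.

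**2. Which records are classified differently?**

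| AE record (otherwise within the time window) | Protocol 13.3 | SAP 8.5.1 |
|---|---|---|
| Starts on or after Day 1 | TEAE | TEAE |
| Started before Day 1, did not worsen | Not a TEAE | Not a TEAE |
| Started before Day 1; worsening entered as a new record with its own start date | TEAE | TEAE |
| Started before Day 1; same record, severity rose on or after Day 1 | TEAE | **Not a TEAE** |

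Only the last row differs.

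**3. Does date imputation close the gap?** In part. SAP 8.5.1 states: "Missing and/or incomplete dates for AEs are imputed in a manner resulting in the earliest onset within the Treatment Period and the longest duration". The imputed start is the minimum of (a) the later of earliest possible start and first dose, (b) latest possible start, and (c) latest possible stop. Take an illustrative Day 1 of 15 March 2011 and an event still ongoing then:

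- Wholly missing: min(15 Mar 2011, 1 Jan 3000) = 15 Mar 2011, counted.
- Year 2011 only: min(15 Mar 2011, 31 Dec 2011) = 15 Mar 2011, counted.
- March 2011 only: min(15 Mar 2011, 31 Mar 2011) = 15 Mar 2011, counted.
- Year 2010 only: min(15 Mar 2011, 31 Dec 2010) = 31 Dec 2010, not counted.

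The gap is therefore confined to records whose dates, complete or partial, put the start before Day 1.

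**4. Which outputs depend on the rule?** SAP 12.2 lists 9 + 16 + 4 + 11 = 40 adverse event tables (14.3__1.2.1 to 1.2.4). Two are AET001, affected only in their TEAE rows. Two are AET005, which 8.5.1 selects by the study-termination field, so the effect depends on how the TEAE label is read. The other 40 − 2 − 2 = 36 rest wholly on TEAE status. The Narrow Polyneuropathy Subset (SAP 8.1.1) also requires a TEAE.

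**5. Where would such an event still appear?** In AEL001. If serious, it is also in AEL004 and the AET001 row for any SAE. If fatal, it is also in AEL003 and the AET001 row for any AE leading to death.

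**6. Scale.** With the planned 275 subjects as denominator, one omitted subject is 1/275 = 0.36 percentage points. That is the most it can be for a given term in a full-sample table of that size, since a subject with another TEAE of the same preferred term is already counted. US-subset, subgroup and by-year tables can have smaller denominators, where one subject weighs more.

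**The case against.** The strongest reply is that no effect has been shown, and that start-only may be the workable form of the protocol rule. SAP 8.5.1 lists one start date, one stop date and one severity per AE, with no date of worsening. On that list, a worsening can be dated only if it was entered as a new record, and such a record is already counted. Several passages are compatible with that practice. Protocol 11.1.8 says "Any abnormalities or symptoms identified during treatment will be recorded as adverse events", SAP 8.5.5.7 says "Any abnormalities or symptoms identified will be reported as adverse events", and the SAP's coding example is a verbatim term for worsening Parkinson's disease.

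The pre-treatment interval may also be short. Baseline is the final visit of the previous study, drug is dispensed at Baseline, and SAP 6.4.1 sets Day 1 to the first dispensing date. Protocol 12.1.1 brings "AEs which occur in the specified pre-treatment through the follow-up period, regardless of the interval prior to the first administration of the study drug" into AE recording, but no passage says that AEs ongoing from Study 3003 or 3004 were carried into the 3005 AE data.

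Much of this stands. It limits the size and argues against an elaborate remedy. It does not remove the conflict: none of these passages requires a new record for a worsening. If one severity per AE was the reason for the narrower rule, section 10.1 is where to say so.

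A reader might go further and infer that all AEs ongoing at entry are wrongly excluded. They are not: without worsening they are not TEAEs under either document. Nor would the affected events vanish from the report, as step 5 shows.

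**Conclusion.** The point holds as an undeclared departure from the protocol. SAP 8.5.1 omits a class of event that protocol 13.3 counts, and any resulting error lowers the main safety summaries. The number of subjects affected cannot be determined. It is zero if every worsening was entered as a new record, or if the 3005 data hold no pre-Day 1 AE that worsened. The 0.36-point figure assumes the planned 275 as denominator and describes one subject; it is not an estimate of the bias. A reader might infer that TEAE rates are materially understated, or that the definition was narrowed on purpose. The documents support neither. The correction is still worth making, because it is cheap and the SAP also governs the final study report.

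**What to change.** Restore the worsening-in-severity limb in SAP 8.5.1, and say in 6.4.6 that an AE worsening on or after Day 1 belongs to the Treatment Period. State that a worsening entered as a new AE record counts from its own start date. Also count as a TEAE any pre-Day 1 record that the 3005 data themselves show to have risen in severity on or after Day 1. Do not reconstruct severity from the earlier studies, which the SAP does not plan to retrieve, and do not add columns to the by-year tables.

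If the start-only rule is kept because the data hold one severity per AE and no worsening date, declare and justify that departure in SAP 10.1.

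The cost is a small wording change and some derivation work. TEAE percentages would be the same or slightly higher. Comparability with the earlier interim output may be reduced; its definition is in SAP Version 2, which is not among the documents.

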6.4 Day Numbers, Study Periods and Visit Windows: Related Definitions

6.4.1 General Definitions

Assessment days will be related to the date of the first infusion of 3005 study drug (First 3005 LCIG Infusion). Baseline is defined in Section [6.4.5](#) (Baseline Period). The Cutoff Date for the 2015 interim analysis will be 30 September 2015. Assessments and/or measurements performed after the Cutoff Date, adverse events or device complications with start dates after the Cutoff Date, and concomitant medications with start dates after

the Cutoff Date will not be included in the 2015 interim analysis. No cutoff date will be applied to the analysis for the final CSR.

The following reference dates will be defined for all subjects in the All Subjects Consented subject sample defined in Section 8.1.1.

- **Date of the First 3005 LCIG Infusion (Day 1, RFSTDTN):**

The actual dates of study drug administration are not recorded in the 3005 database. The dates when 3005 study drug is dispensed are recorded in the DA raw data panel. For analysis, the date of the first 3005 LCIG infusion will be defined as the first date that 3005 study drug was dispensed to the subject. The visit date recorded in the DM raw data panel will be used if the date the first study drug was dispensed is not available.

The date of the first 3005 LCIG infusion will be defined as Day 1 and is the key variable RFSTDTN and is used in the calculation of relative days.

- **Date of the Last 3005 LCIG Infusion (RFENDTN):**

For subjects who have prematurely discontinued or completed the study, the date of the last 3005 LCIG infusion will be the earliest of 1) the date of last study drug administration collected on the DS raw data panel, 2) the date of discontinuation or study completion collected on the DS raw data panel and 3) the Cutoff Date (interim analysis only).

For the 2015 interim analysis, the date of the last 3005 LCIG infusion for all ongoing subjects will be the Cutoff Date.

- **Duration of 3005 LCIG Infusion (LDA):**

The Duration of 3005 LCIG Infusion or exposure to treatment is equal to the day number of the Last 3005 LCIG Infusion (LDA) and is derived as follows from the previous two dates:

$$\text{LDA (days)} = (\text{Date of the Last 3005 LCIG Infusion [RFENDTN]} - \text{Date of the First 3005 LCIG Infusion [RFSTDTN]}) + 1$$

LDA then indicates the relative day of the last 3005 LCIG infusion for each subject.

- **Date of Last 3005 PEG-J Exposure (RFENDT2N):**

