LCIG is administered as part of a therapeutic system that includes devices and implantation procedures. Subjects who discontinue LCIG therapy are to have their PEG-J removed.

For subjects who have prematurely discontinued or completed the study, and have reported a final PEG-J removal on the DI raw data panel that is after their last day of study drug administration and before the Cutoff Date (interim analysis only), their date of last 3005 PEG-J exposure will be the date of PEG-J removal. For all other subjects who have prematurely discontinued or completed the study, their date of last 3005 PEG-J exposure will be the earlier of 1) the date of discontinuation or study completion collected on the DS raw data panel, and 2) the Cutoff Date (interim analysis only).

For the 2015 interim analysis, the date of the last 3005 PEG-J exposure for all ongoing subjects will be the Cutoff Date.

The date of the last 3005 PEG-J exposure is the key variable RFENDT2N.

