$$\text{CM Stop Day} = (\text{CM Stop Date} - \text{Start of 3005 LCIG Infusion} + 1)$$

A subject will be considered to have taken a specific CM during an interval if:

- the CM Start Day is within the study day range for the interval and was not greater than the day of the last 3005 LCIG infusion, or
- the CM Start Day is less than the lower limit of the study day range and the CM Stop Day is later than the lower limit of the study day range or missing.

Note that this definition assumes that a missing CM Stop Day is an indication that the use of the CM is ongoing. The denominator for percentage calculations for each interval will be the number of subjects whose last day of 3005 LCIG infusion was within or after the interval day range.

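### By-year AE prevalence (AET014) and anti-parkinsonian medication use (CMT002) count subjects who are not in that year's denominator, which overstates Years 2 to > 5

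*SAP*

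**What the plan says.** **Adverse events (SAP 8.5.1).** A subject counts towards a year's prevalence if an occurrence of the preferred term starts in that year, or if the subject is one "who had an earlier treatment-emergent occurrence of the PT that had not ended prior to the start of the study day range". The "denominator for both incidence and prevalence percentage calculations will include all subjects whose Treatment Period End Day is within or greater" than the day range of the year. Treatment Period End Day is the last PEG-J exposure plus 30 days. Missing AE dates are imputed, but "the Stop Date will not be imputed if the event is reported as" Ongoing.

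**Concomitant medication (CM; SAP 8.2.4).** Use in an interval is met in one of two ways. The first bullet needs a CM Start Day "within the study day range for the interval and was not greater than the day of the last 3005 LCIG infusion". The second applies when "the CM Start Day is less than the lower limit of the study day range and the CM Stop Day is later than" that lower limit, or is missing. The SAP adds that "this definition assumes that a missing CM Stop Day is an indication that the use of the CM is ongoing". The denominator holds subjects whose last 3005 infusion falls in or after the interval.

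**Interim (SAP 6.4.1).** For the 2015 interim, "the date of the last 3005 PEG-J exposure for all ongoing subjects will be the Cutoff Date", and likewise "the date of the last 3005 LCIG infusion for all ongoing subjects will be the Cutoff Date".

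The rules feed three AET014 tables (`14.3__1.2.1.9`, `14.3__1.2.2.6`, `14.3__1.2.2.11`) and the two by-year CMT002 tables (`14.1__1.4.2`, `14.1__2.3.2`).

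**The concern.** In both rules the carry-forward limb has no end, while the denominator shrinks as subjects leave. Leaving is part of the design: under SAP 8.1.5 subjects stay until commercial LCIG reaches them, so transfers leave as well as drop-outs. Anyone who goes with an open event or drug remains in later numerators. At the interim this also happens to subjects still on treatment who had not reached a year by the Cutoff Date, because their exposure is closed at that date and their open events are not.

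The CM text shows that a limit was thought necessary: the first bullet stops at the last infusion, and the carry-forward bullet does not.

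Protocol 13.1 makes long-term safety the primary statistical objective. These tables are where a reader would look for persistence of events, including procedure and device events of special interest, and for continuing need of other PD drugs. An upward trend produced by departures would look like accumulating toxicity or growing co-medication.

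**Working it through.** The plan states no figure to reproduce. The fault follows from the rules alone; its size needs assumed rates.

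**1. One subject.** Year 1 is Days 2 to 365 and Year 2 starts on Day 366 (SAP Table 3). Let last infusion and last PEG-J exposure be Day 300, with an AE starting on Day 250 and Ongoing, and a PD drug started on Day −100 with no stop. Treatment Period End Day = 300 + 30 = 330, which is below 366.

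| | Numerator | Denominator |
|---|---|---|
| AE prevalence | Years 1, 2, 3, 4, 5, > 5 | Year 1 only |
| CM use | Years 1, 2, 3, 4, 5, > 5 | Year 1 only |

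**2. Is any other limb at fault?** No. A treatment-emergent AE must start by last PEG-J exposure + 30 days, so one starting within a year implies an End Day in or after that year. The first CM bullet is protected by its cap. The mismatch comes only from the carry-forward limbs. It only adds to numerators, and it begins in Year 2.

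**3. CM, final analysis.** Let u be true use, a the yearly leaving proportion, f the share of leavers' stop dates left open, and k the year. The share still present is (1−a)^(k−1), and leavers add u × f × [1 − (1−a)^(k−1)] to the numerator. The printed value is

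u × [1 + f × ((1−a)^−(k−1) − 1)].

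Year 5 (k = 5), u = 60%:
- a = 5%, f = 1: 60 / 0.95⁴ = 60 / 0.8145 = 73.7%
- a = 10%, f = 1: 60 / 0.6561 = 91.4%
- a = 15%, f = 1: 60 / 0.5220 = 114.9%
- a = 15%, f = 0.5: 60 × (1 + 0.5 × 0.9157) = 87.5%
- a = 15%, f = 0.25: 60 × (1 + 0.25 × 0.9157) = 73.7%

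With u = 30%, a = 15%, f = 1: 30 / 0.5220 = 57.5%.

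**4. AE prevalence, final analysis.** Day-level simulation, 500,000 subjects per scenario. Onsets are Poisson with recurrence; leaving times are exponential; a share of events is permanent and the rest last a mean of 60 days; events open at exit stay Ongoing unless stated; follow-up is capped at 7 years. Monte Carlo error is about 0.1 to 0.2 points. Year 5, 10% onset per year unless stated:

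| Permanent | Leaving/yr | As written | Restricted to denominator |
|---|---|---|---|
| 0% | 15% | 12.4% | 10.8% |
| 5% | 15% | 14.8% | 12.5% |
| 20% | 5% | 19.4% | 18.2% |
| 20% | 10% | 20.4% | 17.8% |
| 20% | 15% | 22.3% | 17.8% |
| 20%, half of open events left Ongoing | 15% | 20.0% | 17.7% |
| 20%, onset 5%/yr | 10% | 10.5% | 9.2% |

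**5. AE prevalence, 2015 interim.** Entry dates are not given. Two ranges were assumed: 3.4 to 7 years before cut-off (04 May 2012 to 30 September 2015 is 3.41 years; the last visit label is Month 84) and 2 to 6 years. Onset is 10% per year, with 20% permanent.

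| Entry before cut-off | Leaving/yr | Year 5 | > Year 5 |
|---|---|---|---|
| 3.4–7 years | 0% | 18.1 v 16.7% | 26.5 v 19.5% |
| 3.4–7 years | 15% | 22.9 v 16.1% | 38.2 v 19.0% |
| 2–6 years | 0% | 22.7 v 16.0% | 37.8 v 15.6% |

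**6. CM, 2015 interim, nobody leaving.** Printed value = u / share reaching the year. With entry 3.41 to 7 years before cut-off, the share reaching Year 5 is (7 − 1461/365) / 3.59 = 0.835 and > Year 5 is (7 − 1826/365) / 3.59 = 0.556. True use of 60% prints as 71.9% and 107.8%.

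**The case against.** **Intent.** SAP 6.4.7 places time after the Treatment Period in a Post-Treatment Period, 8.2.4 defines concomitant medication by use in the Treatment Period, and the CMT002 entry in 9.6 refers to the Safety Sample during the interval. A programmer might therefore restrict the numerator unprompted. That is fair evidence of intent. But none of these passages changes the explicit counting rules, and SAP 4.0 says the plan is there to guide programming.

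**Recorded stop dates.** Protocol 12.1.2 asks for follow-up until events resolve or lose clinical significance, so transient events may acquire true stop dates. AE stop dates that are missing but not Ongoing are generally capped at the last drug administration. This objection has force. With true stop dates for transient events, 10% onset and 15% leaving per year, Year 5 becomes 10.9 v 10.8% with no permanent events and 13.5 v 12.6% with 5% permanent. At 20% permanent it is still 21.1 v 17.7%. The same protocol section lets follow-up of chronic conditions end once they are characterised, and persistent events are what a prevalence table is meant to show.

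**Inputs.** The interim entry ranges are guesses: neither the earlier cut-off nor the open-ended Month 84 window fixes enrolment. CM values above 100% need high use, substantial attrition (or, at the interim, many subjects short of the year) and nearly all stops open. They would be caught in table review; smaller errors would not.

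**Reach.** These are descriptive tables, and Protocol 13.4 sets no alpha level. That limits the consequence but does not correct the tables.

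**Conclusion.** The concern holds. As written, both carry-forward rules count subjects outside the year's denominator, and the error is always upward from Year 2 onward. The size depends on leaving rates, entry dates, persistence and how often stops are left open, none of which the documents give.

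For AEs in the final analysis, the Year 5 excess is under one point for mostly transient terms with recorded stops. It is roughly 1 to 4.5 points (19.4 v 18.2% up to 22.3 v 17.8%) when a fifth of events are permanent, onset is 10% per year and leaving is 5% to 15% per year. Interim distortion could be larger in the last intervals. Medication tables are more exposed, because a missing stop counts as ongoing and baseline use may be high.

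Overall AE, serious AE and discontinuation tables, by-year incidence (AET011) and the first-day CMT002 tables do not use these limbs. The point is worth correcting because it concerns the long-term safety display, but it threatens no test.

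A separate, minor gap: an AE starting on Day 1 belongs to the Treatment Period (SAP 6.4.6), but Year 1 starts on Day 2 (Table 3), so a first occurrence on Day 1 falls in no incidence year. It should affect few subjects and was not quantified.

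**What to change.** Add to the AE prevalence numerator in SAP 8.5.1, and to the second CM bullet in 8.2.4, the condition that the subject also meets the denominator requirement for that Treatment Year. Apply it to the final tables, and to any re-issue of the October 2015 interim tables. As a minor tidy-up, start Year 1 at Day 1 for events assigned to the Treatment Period.

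The cost is one clause in two places and a programming filter on existing data. No new data are needed.
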